5.2. Phase II

The study product will be dispensed only to those subjects who will indicate that they volunteerize to participate in this phase of the study.

At Phase II subjects with xerostomia and that are willing to try the study product, will be requested to use it with no training, except for their understanding of the User Manual (internal labeling). Those subjects will use the study product in a supervised clinical setting. Subjects who report any discomfort will be offered the option to pause and remove the device upon such a request.

Correct use verification will be performed by the study investigators. Subjects will answer questions regarding product use, clarity of the IFU, ease of use, etc. Subjects will also receive an exam of their oral cavity.

6. Study Design

Study Type:	Interventional (Clinical Trial)
Enrollment:	Phase I: 16 participants, 8 with xerostomia and 8 without xerostomia
	Phase II: 16 participants with xerostomia (may include participants in Phase I with xerostomia)
Allocation:	N/A
Intervention Model:	Single Group Assignment
Masking:	None (Open Label)
Primary Purpose:	Human Factor Validation - Usability Engineering assessment for OTC labeling
Official Title:	SaliPen Usability Engineering Study for OTC labeling
Study Start Date:	TBD

According to the FDA Guidance document “Applying Human Factors and Usability Engineering to Medical Devices”, a sample of 15 people to detect most of the problems in a user interface constitutes a practical minimum number of participants for human factors validation testing. This sample size theoretically provides the best possibility of detecting user interface design flaws while limiting the amount of resources required.

7. Arms and Interventions

Arm	Intervention/treatment
Experimental: Use of SaliPen medical device	Use according to self-decision.

8. Features to be studied

The points of interaction between the user and the device (User Interface) will be evaluated, including:

- the elements of the device with which the user interacts (i.e., those parts of the device that users see and touch), and
- the IFU (including packaging, labeling, User Manual, etc.).

The following parameters will be studied:

- Hazard: Potential source of harm, if any.
- Use error: User action or lack of action that was different from that expected by the manufacturer.

9. Outcome Measures

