1. Percentage of participants who appropriately will self-select the study product for use under simulated OTC conditions [Phase I]. Following the standard norms for the Rx-to-OTC switch process, this outcome is a validation of potential consumers' ability to self-diagnose the condition and to decide that treatment with the product is appropriate for them.
2. Percentage of participants who correctly will use the study product when dispensed under simulated OTC conditions [Phase II]. Correct use means that the participants will demonstrate the use of the study product according to the guidelines outlined in the User Manual. Following the standard norms for the therapy of Rx-to-OTC switch process, this outcome is a validation of potential consumers' ability to self-treat with the product according to the product's supplied IFU.

10. Eligibility Criteria

Ages Eligible for Study: 18 years of age and older for Phase I and Phase II

Genders Eligible for Study: Female and male

10.1. Inclusion criteria:

- 1- For Phase I: 8 subjects with xerostomia and 8 without that are 18 years old or older
- 2- For Phase II: Subjects with xerostomia that are 18 years old or older

10.2. Exclusion criteria:

- 1- For Phase I:
 - Children and adolescents (persons under 18 years of age)
 - Persons with experience in the use of SaliPen

2- For Phase II: Subjects for whom the study product is not indicated and/or do not agree to participate in Phase II. For the avoidance of doubt, the following conditions are exclusion criteria:

- Persons with experience in the use of SaliPen
- Children and adolescents (persons under 18 years of age)
- Epileptic disorder
- Persons that are allergic to the surface materials of the device
 - Electrodes: coated with gold
 - Body: made of methyl vinyl silicone rubber
- Use of a pacemaker
- Pregnancy
- Psychiatric or psychological disorders
- Involuntary muscle movement disorder (such as Parkinson's)
- Neurologic disorder in head and neck area

11. Reportable Events

An adverse event (AE) is defined as any untoward medical occurrence in a subject during the investigation. Any findings will be documented on the AE CRF.

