14.5. Subject Confidentiality

All subject data will be identified only by a subject identification number and date of birth.

15. Guide for participants

Phase I - Self-Administered Questionnaire

I.D.: _____ DATE: _____

Please read the cover and the back cover of the device and answer the following questions:

1. Is the device for Dry Mouth Relief?

- Yes
- No

2. Does the device fit your needs?

- Yes
- No

3. If the device fits your needs, please check a box (only one):

- I can use the device.**
- I cannot use the device because, either:**
 - I'm under 18 years of age.
 - I suffer from epileptic disorder.
 - I'm allergic to gold or silicone rubber.
- I need a professional consultation before buying the device because, either:**
 - I use a pacemaker.
 - I'm pregnant.
 - I suffer from a psychiatric or psychological disorder.
 - I suffer from an involuntary movement disorder (for example Parkinson's disease).
 - I have a neurologic disorder in the head and neck area (for example trigeminal neuralgia).

Phase II - Interviewer-administered questionnaire

I.D.: _____ DATE: _____

Please read the user manual and hold the device.

Firstly, your oral cavity will be examined.

Next, you will be asked the following questions and to perform the following tasks:

- 1. How many times can you use the device in a day and how many minutes (maximum time) you can use the device in one session? (See page 2)**
- 2. How do you turn ON and OFF the device? (See page 6)**
- 3. How do you insert the device in your mouth? (See pages 7, 8 and 9 and watch the video “How to use the SaliPen device to stop dry mouth”)**
- 4. How do you take the device out of your mouth? (See pages 7, 8 and 9)**
- 5. How do you detach and reattach the white extraoral command unit from the blue intraoral stimulating unit? (See page 6)**
- 6. Did you experience discomfort with the SaliPen in your mouth?**
- 7. Did you experience difficulties in using the SaliPen?**

Finally, your oral cavity will be examined again.

16. Evaluation Sheets

Phase I

Subject I.D.: _____

EVALUATOR NAME: _____

Date: _____

Step 1: Anamnesis taken by the evaluator

Ruling	Parameters	yes	no
Indication	Xerostomia		
Contraindications	Under 18 years old		
	Epileptic disorder		
	Allergy to gold		
	Allergy to silicone		
Precautions – medical advice recommended before purchase	Pacemaker		
	Pregnant		
	Psychiatric or psychological disorder		
	Involuntary movement disorder (e.g., Parkinson's disease)		

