Gingival Mucosa			_____
Edentulous Ridge/Retromolar area			_____
Tongue			_____
Sublingual Area/floor of mouth			_____
Submandibular area			_____

Step 2: Assessment of subject performance
EVALUATOR NAME: _____

DATE: _____

Please evaluate how the participant addresses the following questions/tasks:

Questions	Participant's answer	Correct answer	Success (1) / Failure (0)
1. How many times in a day and how many minutes (maximum time) you can use the device in one session?			
Tasks	Evaluation		Success (1) / Failure (0)
2. How do you turn on ON and OFF the device?			
3. How do you insert the device in your mouth?			
4. How do you take the device out of your mouth?			
5. How do you detach and reattach the white extraoral command unit from the blue intraoral stimulating unit?			
Subject assessment (place an x where relevant for you) Note: Success (1) is meant if options 2 or 3 were chosen Failure (0) is meant if option 1 was chosen			Success (1) / Failure (0)
6. Did you experience discomfort with the SaliPen in your mouth?	1- Severe discomfort 2- Moderate discomfort 3- No discomfort		
7. Did you experience difficulties in using the SaliPen?	1- Severe discomfort 2- Moderate discomfort 3- No discomfort		

Summary evaluation:
Total questions/tasks/self-assessments: 7

Number of points: _____

Passed? (minimum 6 points):

Yes
 No

Step 3: Oral soft tissue examination

EVALUATOR NAME: _____

DATE: _____

	Normal	Abnormal	If Abnormal, please specify findings
Labial Mucosa (including lips)			
Buccal Mucosa			
Mucogingival Folds			
Gingival Mucosa			
Edentulous Ridge/Retromolar area			
Tongue			
Sublingual Area/floor of mouth			
Submandibular area		

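### The Phase II script and score sheet do not require or record an actual use of the device, so a participant can be scored 7 of 7 on correct use without an observed powered use

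*Combined protocol and SAP*

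**What the plan says.** Section 5.2 states that Phase II subjects "will be requested to use it with no training, except for their understanding of the User Manual (internal labeling"), in a supervised clinical setting, with the option to pause and remove the device if it is uncomfortable. Study investigators verify correct use. Section 9, Outcome 2, sets the standard: "Correct use means that the participants will demonstrate the use of the study product according to the guidelines outlined in the User Manual". It presents this outcome as validating that consumers can treat themselves from the supplied instructions.

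Section 8 lists what is to be detected, including: "Use error: User action or lack of action that was different from that expected by the manufacturer".

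The section 15 guide for Phase II opens with "Please read the user manual and hold the device". After a first oral examination it continues: "Next, you will be asked the following questions and to perform the following tasks". Item 1 asks for the daily number of uses and "how many minutes (maximum time) you can use the device in one session? (See page 2"). Item 2 is "How do you turn ON and OFF the device? (See page 6"). Items 3 to 5 cover insertion, removal, and detaching and reattaching the two units, again with page references (and a video for item 3). Items 6 and 7 ask about discomfort and difficulty. A second oral examination closes the visit.

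The section 16 sheet scores the same seven items 0 or 1 and passes a subject with at least 6 points. The section 13 task list matches it, with most Phase II tasks worded as things the user knows how to do.

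**The concern.** Outcome 2 is about using the product. The forms that generate its data score handling steps one at a time, each on request. Nothing in them says that the device must be switched on while in the mouth, that a session must be run, or that its occurrence must be noted.

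Two things are at stake:

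- **Meaning of a pass.** A subject who counts towards the 85% success rule may not have been seen using the device as a stimulator. The record would not distinguish that subject from one who was.
- **Detectable errors.** Section 8 counts a lack of action as a use error. When the interviewer names each task in turn and points to the relevant page, errors between tasks are hard to detect: skipping a task, doing tasks in the wrong order, or not following the manual's own session limit. An unaided OTC user could make these errors.

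The discomfort and difficulty ratings and the second oral examination are affected too. Without a record of exposure, a benign rating or a normal second examination is hard to interpret.

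**Working it through.** **Inputs.** The seven items (sections 15 and 16); the 85% per-subject rule and the 85% study rule (section 13); the 6-point pass mark (section 16); 16 Phase II subjects (section 6).

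**Step 1: reproduce the plan's pass mark.** 0.85 × 7 = 5.95, rounded up to 6. Check: 6/7 = 85.7% passes and 5/7 = 71.4% fails. The sheet's minimum of 6 agrees with section 13. At study level, 0.85 × 16 = 13.6, rounded up to 14 subjects (14/16 = 87.5%; 13/16 = 81.3% falls short).

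**Step 2: read each scored item for a requirement that the device be ON in the mouth.**

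| Item | What is scored | ON in the mouth required by the wording? |
|---|---|---|
| 1 | Stating the daily and per-session limits | No, a knowledge question |
| 2 | Turning ON and OFF | No, can be shown in the hand |
| 3 | Insertion | No, power state not mentioned |
| 4 | Removal | No, power state and elapsed time not mentioned |
| 5 | Detaching and reattaching the units | No |
| 6 | Discomfort with the device in the mouth | No, stimulation not mentioned |
| 7 | Difficulties in using the device | No, success unless the most severe option is chosen |

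Count: 0 of 7. The section 13 Phase II tasks give the same result.

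**Step 3: find the highest score open to a subject with no powered use.** Suppose the subject states the limits correctly, shows ON and OFF in the hand, inserts and removes the device unpowered, separates and rejoins the units, and does not choose the most severe option on items 6 and 7. The score is 1+1+1+1+1+1+1 = 7, against a pass mark of 6.

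**Step 4: what depends on exposure.** Item 6 asks "6. Did you experience discomfort with the SaliPen in your mouth", and item 7 asks about difficulties in use. Together they are 2 of 7 points (2/7 = 28.6%). The second oral examination follows with no minimum exposure stated before it.

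**Step 5: look for a record of use.** The Phase II sheet has identifiers, evaluator name, date, examination findings, answers, evaluations and scores. It has no field for whether use occurred, its start and stop, or early removal.

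**The case against.** The strongest reply is that the plan does prescribe use. Section 5.2 says so directly, section 7 names the arm as use of the device, the synopsis refers to the device that Phase II participants will use, and items 6 and 7 presuppose use. Nothing says that the questionnaire replaces section 5.2. Items 2 to 4 are also tied to manual pages and a video that are not in the documents. If those pages have the user switch on as part of insertion, following item 3 would itself be powered use.

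Much of this stands, and it rules out several stronger readings that a reader might infer:

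- *That no subject will use the device powered, or that adherence to the session limit will be observed in none of the 16.* The documents show what the forms require, not what the site will do.
- *That ON and OFF must both be completed before insertion.* The items are numbered, but no text says each must be finished before the next or that the device is off during items 3 and 4.
- *That omissions or order errors cannot appear.* Items 3 and 4 each refer to three manual pages, and a missed or misordered step within a task can still be seen and scored.
- *That a safety outcome is undermined.* The second oral examination is neither scored nor one of the two outcomes in section 9.

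Section 13 also chooses discrete tasks openly, which is a recognisable approach to task analysis.

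The reply does not close the gap. The scored data come from sections 15 and 16, and those can be completed in full without the use that section 5.2 describes. If the manual does call for powered use, practice could still differ between evaluators without the record showing it. Prompting each task with a page number also remains a weak test of unaided use.

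**Conclusion.** The point holds as a mismatch between the stated outcome and the instruments that measure it. No scored item (0 of 7) requires powered use in the mouth, a subject can score 7 against a pass mark of 6 without one being observed, and 2 of 7 points depend on an exposure that is not recorded. Errors between tasks are hard to detect; errors within a task remain visible. It does not follow that Phase II tests only isolated handling, because section 5.2 intends more.

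This rests on reading the items as worded, without the User Manual or the video. If those require powered use, observed conduct may be closer to section 5.2, but the forms would still neither demand nor document it. No sample-size or error-rate figure bears on the point. The change should be made before Phase II starts, because use that was not recorded at the visit cannot be reliably reconstructed later.

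**What to change.** Reconcile sections 13, 15 and 16 with section 5.2, in this order:

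1. First oral examination and reading of the manual.
2. One request to use the device as the manual describes, without item prompts or page references.
3. The evaluator already present scores items 2 to 4 from what is observed, under a stated rule for which item fails on an order error or an ON/OFF error, and records start, stop and any early removal.
4. Items 1 and 5, then items 6 and 7.
5. Second oral examination.

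The manual's own limits and the existing option to pause or remove the device stay unchanged. No session length is proposed.

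Scoring within items 2 to 4 keeps the total at 7. Adding an eighth item would move the pass mark to 7 of 8 (0.85 × 8 = 6.8, rounded up), and a subject could miss that item alone and still pass at 7/8 = 87.5%. The same limit applies within seven items: one failed item still leaves 6 of 7. The recorded use data should therefore be reported alongside the pass rate.

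Cost: changes to one script, one sheet and the task list; an amendment with IRB approval (section 14.4); a somewhat longer visit, by an amount the documents do not allow one to calculate, within the roughly one day planned; and possibly a lower pass rate. No extra subjects or evaluators are needed.

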3.2. The study rationale

- Xerostomia (dry mouth) is the subjective feeling of oral dryness. The diagnosis by the practitioner is mostly relying on the patient's feeling.
- Most patients are elderly, many of them with limited mobility.
- Nowadays, those patients are at high risk for COVID-19 infection, morbidity and even mortality.
- The fear of exposure at the practitioner's clinic to obtain an Rx inhibits them from treating their xerostomia with the SaliPen.
- The cost of getting a prescription is an additional burden.
- The SaliPen is an OTC in other parts of the world for years.
- The performance of potential American users of an OTC SaliPen device will be evaluated in this usability study.

As a result, many patients leave their oral dryness untreated, with the well-known consequences of poor oral functions, oral health, daily suffering, and more.

4. Brief Study Description

This Human Factors Validation Testing will assess user interactions to verify the capability of potential users to assess if the study product fits their needs and if they can use it correctly based on the provided Information For User (IFU)?

More specifically, this is a non-comparative case series study and is subdivided into two major parts. Those parts are:

- 1- Phase I: aimed at testing if, based on the IFU, the potential subjects can decide whether the study product is or is not appropriate to treat their condition and,
- 2- Phase II: aimed at assessing whether the users can use the study product correctly without counseling by a health care provider.

Condition or disease	Intervention/treatment
Xerostomia	SaliPen

5. Detailed Study Description

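### The Phase II form points subjects to the manual page for each of scored items 1-5 and, for item 3, to a how-to video that the protocol names nowhere else

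*Combined protocol and SAP*

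**What the plan says.** Section 15 (Guide for participants) contains an interviewer-administered Phase II questionnaire. It opens with "Please read the user manual and hold the device", places an oral examination next, and then lists seven numbered questions and tasks addressed to the subject. Question 1, on the daily number of uses and the session length, ends "you can use the device in one session? (See page 2". Questions 2 and 5 carry a reference to page 6, and question 4 to pages 7-9. Question 3, on inserting the device, says "See pages 7, 8 and 9 and watch the video" and gives the video's title. Questions 6 and 7 carry no reference. The video is mentioned nowhere else.

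The evaluation sheet in section 16 (Phase II, Step 2) scores the same seven items 1 or 0. Items 1-5 appear there without page or video references.

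Other sections set the conditions of the test:

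- Section 4 says Phase II is "aimed at assessing whether the users can use the study product correctly without counseling by a health care provider".
- Section 5.2 says subjects "will be requested to use it with no training, except for their understanding of the User Manual (internal labeling").
- Section 8 lists "the IFU (including packaging, labeling, User Manual, etc".) as part of the user interface under study.
- Section 9 gives the Phase II outcome as "Percentage of participants who correctly will use the study product when dispensed under simulated OTC conditions [Phase II"], where correct use means that participants "demonstrate the use of the study product according to the guidelines outlined in the User Manual".

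**The concern.** Phase II is meant to show that a purchaser can use the device from the supplied instructions alone. The form raises two separate problems.

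**Video.** A how-to video is neither the User Manual nor, on any explicit statement, part of the IFU. If purchasers do not receive it, placing the device in the mouth is scored with help they will not have. If they do receive it, the narrower issue is that subjects are told to watch it rather than finding it themselves.

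**Page references.** Subjects have already been asked to read the manual. A reference beside the question adds only the location of the answer, which a purchaser would have to find. Item 1 is the one item that section 16 classes as a question rather than a task. With page 2 named, it tests look-up of a given page. Items 2-5 are demonstrated, so a reference assists the demonstration but does not replace it. A manual that is hard to navigate could go unnoticed, although section 8 makes the manual part of what is studied.

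Both effects run towards passing, and they act on a primary outcome.

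**Working it through.** **1. Thresholds, from sections 6, 13 and 16.**

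- Subject: 85% of 7 items is 0.85 x 7 = 5.95, so 6 points. This reproduces the minimum on the section 16 sheet (6/7 = 85.7%).
- Phase II: 85% of 16 subjects is 0.85 x 16 = 13.6, so 14 must pass (13/16 = 81.25%, 14/16 = 87.5%).

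**2. How much rests on the cued items.** Items 6-7 can give at most 2 points, so items 1-5 must supply at least 6 - 2 = 4. Five of the seven items (71%) carry a page reference.

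**3. When a cue changes a subject's result.** One miss is allowed, so a cue on item 1 matters only when exactly one other item is missed. Suppose items are independent, items 6-7 are always scored 1, item 1 has success rate p, and items 2-5 each have rate q. Then

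P(subject passes) = q^4 + p x 4(1 - q)q^3.

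With q = 0.95, this is 0.8145 + 0.80 x 0.1715 = 0.952 without the cue and 0.8145 + 0.95 x 0.1715 = 0.977 with it. The gain is 0.15 x 0.1715 = 0.026.

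**4. From subject to study.** P(Phase II passes) is the binomial probability of at least 14 passes among 16. The documents give no cued or uncued rates, so every rate below is an assumption.

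Item 1 alone rises from 0.80 to 0.95:

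| Items 2-5 (q) | Subject passes | Phase II passes |
|---|---|---|
| 0.98 | 0.983 to 0.994 | 0.998 to 1.000 |
| 0.95 | 0.952 to 0.977 | 0.961 to 0.995 |
| 0.90 | 0.889 to 0.933 | 0.743 to 0.913 |
| 0.85 | 0.817 to 0.872 | 0.417 to 0.663 |

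Item 1 rises as above, and items 2-5 also rise by 0.02:

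| Items 2-5 | Subject passes | Phase II passes |
|---|---|---|
| 0.95 to 0.97 | 0.952 to 0.989 | 0.961 to 0.999 |
| 0.90 to 0.92 | 0.889 to 0.953 | 0.743 to 0.963 |
| 0.85 to 0.87 | 0.817 to 0.898 | 0.417 to 0.782 |

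Item 3 alone (the video item) rises from 0.85 to 0.95, with items 1, 2, 4 and 5 at q:

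| Other four items (q) | Subject passes | Phase II passes |
|---|---|---|
| 0.95 | 0.960 to 0.977 | 0.976 to 0.995 |
| 0.90 | 0.904 to 0.933 | 0.806 to 0.913 |
| 0.85 | 0.835 to 0.872 | 0.495 to 0.663 |

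**5. Sensitivity.** With items 6-7 at 0.95 each instead of 1, the item 1 rise moves the Phase II probability from 0.872 to 0.968 (q = 0.95), 0.573 to 0.795 (q = 0.90) or 0.273 to 0.490 (q = 0.85).

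**The case against.** **Timing.** Section 15 is headed as a guide for participants and begins with reading the manual, so the references might be an advance reading guide. The scoring sheet in section 16 has none. The protocol does not say whether the references are shown during scoring, or whether the manual is open or closed then. That gap is real. But the references sit inside the interviewer's questionnaire, attached to the questions put to the subject, so run as written they accompany the questions. Even as an advance guide they would tell subjects which pages hold the tested answers.

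**No breach.** A page number supplies no answer, is not counseling, and points only to material that section 5.2 allows. This stands: the page references contradict no passage. The case against them is that they make the test easier than the situation it is meant to represent.

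**The video may be IFU.** Section 8's list is open-ended, section 9 refers to the supplied IFU, and the manual, which is not among the documents, may itself direct users to the video. This also stands, so the conflict is conditional. Even then, sections 5.2 and 9 name only the manual in the places that matter and need to be brought into line.

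**The numbers are assumed.** They are. They show when the cues could matter, and not how much they do.

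**Conclusion.** The concern holds. The references on items 1-5, the video instruction and their absence from section 16 are plain in the text. The video conflicts with sections 5.2 and 9 unless it is supplied IFU, which the protocol does not settle. The page references are a design weakness and not a contradiction.

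The direction of any effect is known (towards passing), but its size is not. If users would do very well anyway, the effect is negligible: the item 1 cue adds about 0.002 to the chance of passing Phase II with items 2-5 at 98%. With items 2-5 at 85% it adds 0.663 - 0.417 = 0.246. These figures assume independent items, items 6-7 always scored 1, and a rise in item 1 from 80% to 95%. They are illustrations and not estimates. Because the correction costs so little, the plan should not rely on the favourable case.

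**What to change.** 1. Delete the page references from Phase II questions 1-5 in section 15. State that the manual is freely available to the subject throughout.
2. Delete the video instruction from question 3 unless the video is supplied with, or linked from, the OTC package or manual. If it is, name it as IFU in sections 5.2, 8 and 9 and let subjects find it unprompted.
3. Use the same uncued wording for items 1-5 in sections 15 and 16. Add a mark on the section 16 sheet for any of these items on which the interviewer gave a prompt.
4. If data have already been collected with this form, report the Phase II rate as obtained with page cues and, where it was watched, with the video.

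The cost is a few deletions, one mark on the scoring sheet, a statement on access to the manual and, if the video is IFU, a phrase in each of three sections. Section 14.4 requires IRB approval before use. No extra subjects, visits or analyses are needed, and the thresholds of 6 of 7 and 14 of 16 do not change. The downside is a possibly lower pass rate and slightly longer sessions.

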5.1. Phase I

To simulate an OTC setting, potential subjects will be requested to read the label text on the outside of the study product package (external labeling) and determine whether the study product addresses their needs, without a provider direction or assistance.

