	Neurologic disorder in the head and neck area (e.g., trigeminal neuralgia)		

Step 2: Self-Administered Questionnaire - Subject pre-purchase selection of the study product

Subjects will be asked to read the cover and the back cover of the device package and answer the following questions:

Question / Statement	Participant's answer	Correct answer	Success (1) / Failure (0)
1. Is the device for Dry Mouth Relief?	 Yes  No	 Yes  No	
2. Does the device fit your needs?	 Yes  No	 Yes  No	
3. If the device fits your needs, please check a box (only one):			
I can use the device	 Yes  No	 Yes  No	

Question / Statement	Participant's answer	Correct answer	Success (1) / Failure (0)
I cannot use the device because, either: 
 • I'm under 18 years of age. • I suffer from epileptic disorder. • I'm allergic to gold or silicone rubber. 	 Yes  No	 Yes  No	
I need professional advice before using the device because, either: 
 • I use a pacemaker. • I'm pregnant. • I suffer from a psychiatric or psychological disorder. • I suffer from an involuntary movement disorder (for example Parkinson's disease). • I have a neurologic disorder in the head and neck area (for example trigeminal neuralgia). 	 Yes  No	 Yes  No	

Step 3: Summary evaluation (to be completed by the evaluator)

Total questions/statements for those with dry mouth: 5

Number of correct answers: _____

Total questions/statements for those without dry mouth: 2

Number of correct answers: _____

Passed? (all answers/statements should be correct):

Yes
 No

Phase II

Subject I.D.: _____

Step 1: Oral soft tissue examination

EVALUATOR NAME: _____

DATE: _____

	Normal	Abnormal	If Abnormal, please specify findings
Labial Mucosa (including lips)			_____
Buccal Mucosa			_____
Mucogingival Folds			_____

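### Phase I has the evaluator ask about all nine listed conditions before the self-selection questionnaire, which may cue question 3 in the few participants it is meant to test

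*Combined protocol and SAP*

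**What the plan says.** Section 5.1 describes Phase I as a simulated OTC setting in which potential users read the outside of the package and "determine whether the study product addresses their needs, without a provider direction or assistance". Section 9 presents the resulting percentage as a validation of consumers' own ability to self-diagnose and to judge that the product is appropriate for them.

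The Phase I sheet in Section 16 sets out the procedure in numbered steps. The first is "Step 1: Anamnesis taken by the evaluator": ten yes/no rows, made up of xerostomia, four contraindications and five precautions. The second is "Step 2: Self-Administered Questionnaire - Subject pre-purchase selection of the study product", which holds the package reading and the three questions. Question 3 asks those who say the device fits their needs to tick one of three boxes (can use, cannot use, needs professional consultation), with the listed conditions printed under the last two.

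Scoring in Step 3 differs by group. Participants with dry mouth are scored on five entries. For the others the sheet states "Total questions/statements for those without dry mouth: 2", so question 3 does not count for them. A participant must have every scored entry correct to pass, and Section 13 requires 85% of participants to pass each phase.

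**The concern.** A shopper reading the box has not first been asked by clinic staff about epilepsy, a pacemaker, pregnancy and the rest. A Phase I participant has, if the step numbers are followed. For someone with xerostomia and one of these conditions, the history may bring the condition to mind and signal that it matters. A correct answer to question 3 is then weaker evidence that the label alone did the work.

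These participants are the ones who show whether the label steers people who should not use the device, or should seek advice first, to the right box (Section 13, Phase I Task 3). They may be few, so each of their answers carries weight. The likely direction of any bias is towards success.

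**Working it through.** **Order.** It rests on the step numbers in Section 16. The Phase I participant guide in Section 15 does not mention the history. Nothing in the protocol places it later, assigns it to a different person or states an interval between the steps.

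**Overlap.**
- Step 1 rows: 1 (xerostomia) + 4 (contraindications) + 5 (precautions) = 10, of which 9 are listed conditions.
- Question 3 bullets: 3 + 5 = 8. They cover the same nine conditions, because gold and silicone allergy share a bullet.

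**Who can be affected.** Question 3 is scored only in participants with xerostomia, 8 of the planned 16. Section 10.2 excludes from Phase I only minors and people with SaliPen experience, so adults with any of the other eight conditions can enrol. How many will do so is not in the documents.

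**What must be asked first.** Section 10 needs age, prior SaliPen use and xerostomia status. Prior SaliPen use is not a Step 1 row. Taking xerostomia and age out of the ten rows leaves 10 − 2 = 8 that enrolment does not need.

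**Phase I threshold.** 0.85 × 16 = 13.6, so at least 14 must pass (14/16 = 87.5%; 13/16 = 81.25% falls short).

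**Scale, on assumed rates.** Let k be the number of participants with xerostomia and a listed condition, p their pass probability, and 0.95 the pass probability of everyone else. The chance of meeting the criterion is P(Bin(16 − k, 0.95) + Bin(k, p) ≥ 14).

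- k = 0: P(Bin(16, 0.95) ≥ 14) = 0.957.
- k = 1: p × P(Bin(15, 0.95) ≥ 13) + (1 − p) × P(Bin(15, 0.95) ≥ 14) = 0.9638p + 0.8290(1 − p).
- k = 2: p² × P(Bin(14, 0.95) ≥ 12) + 2p(1 − p) × P(Bin(14, 0.95) ≥ 13) + (1 − p)² × P(Bin(14, 0.95) = 14) = 0.9699p² + 0.8470 × 2p(1 − p) + 0.4877(1 − p)².

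| k | p = 0.75 (no cue) | p = 0.80 (small cue) | p = 0.90 (larger cue) |
|---|---|---|---|
| 0 | 95.7% | 95.7% | 95.7% |
| 1 | 93.0% | 93.7% | 95.0% |
| 2 | 89.4% | 91.1% | 94.3% |

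The larger cue adds 2.0 points with one affected participant and 4.9 with two. The smaller cue adds 0.7 and 1.7 points.

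**Chance that anyone is affected.** If 5%, 10% or 20% of participants with xerostomia had a listed condition (assumed), the chance of at least one among 8 is 1 − (1 − rate)⁸ = 34%, 57% or 83%.

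**The case against.** The strongest objection is that the cue is largely redundant. Question 3 itself shows the participant every condition, already sorted by verdict, and the documents do not say that participants see the sheet's contraindication and precaution headings. This stands, and it is why the added effect may be small or nil. Reordering removes the staff cue and leaves the printed one.

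Second, recording a history is arguably neither direction nor assistance, so Section 5.1 is not strictly contradicted. That is fair. The point is that the order fits poorly with the intended condition and can be avoided.

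Third, the present order has a merit. The history appears to set the correct-answer column, and taking it first keeps that reference free of the questionnaire. A participant who has already ticked that they can use the device might later understate a condition to stay consistent. The wrong choice would then be scored as right, which also favours success. Keeping the evaluator unaware of the answers does not prevent this. It is a real cost of the change, and the documents give no means of weighing it against the gain.

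Fourth, the xerostomia row could cue question 2, which is scored in all 16 participants, and the fix leaves that row first. This is also true. Recruitment to two groups of 8 needs the status before testing, and Section 3.2 defines the condition by feeling ("Xerostomia (dry mouth) is the subjective feeling of oral dryness"), so it will probably have to be asked.

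Finally, if everyone else passes, three participants with a listed condition would have to fail without the cue before the cue alone could change the Phase I result.

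**Conclusion.** The concern holds, as a minor one. The order, the overlap of nine conditions and the restriction of question 3 scoring to participants with dry mouth all follow from the documents, and none of the eight deferrable rows is needed for Phase I enrolment. The cue bears on one decision, in those of 8 planned participants who have a listed condition, a number that may be zero. Its likely direction favours success. Its size cannot be derived from the documents, and the percentages above show scale only because every pass rate and every k in them is assumed. The reading also assumes that the steps are carried out in their numbered order.

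**What to change.** Before the questionnaire, ask only age, prior SaliPen use and xerostomia status. Move the other eight rows to a separate page, completed after the participant hands in the questionnaire. Have the evaluator fill in the correct-answer column from that page before seeing the participant's answers. If the sponsor prefers to keep the full history first, the protocol should give the reason.

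The cost is a split and reordered form, with the history and answer key kept apart from the participant's answers, which now sit in the adjacent column. If the protocol is already approved, the change needs IRB approval (Section 14.4). The risk that the questionnaire colours the later history should be acknowledged. No extra staff or procedure is needed. Phase I involves only reading the package, and the device is dispensed only in Phase II (Section 5.2), so deferring the rows exposes no one to it.
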